6.1.1. Missing and partial data for primary outcome

For the calculation of mean symptom score for particular treatment (statin, placebo, no medication) missing scores ($i < 28$) will be handled by only using study months that have at least 10 of daily symptom scores non-missing. We will perform sensitivity analyses using different thresholds for non-missing scores (such as 14 and 16 non-missing scores) and compare the percentage of missing symptoms scores during the 'pill' months (statin or placebo) versus 'no pill' months. We will assess the temporal pattern of missing symptom scores by comparing the percentage of missing scores at the beginning of the study to the percentages at later study months.

The nocebo effect for an individual participant will be calculated only if he or she has non-missing symptom scores for at least one month of each treatment ($j \geq 1$). If the participant has not recorded any symptom score for one of the three treatments ($j=0$ for statin, placebo, or no pill) the nocebo effect cannot be calculated, and the primary endpoint analysis will exclude that participant.

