8 STATISTICAL AND DATA ANALYSIS

Our study's principal hypotheses will be tested as follows:

Hypothesis 1 will be tested by calculating the proportion of respondents completing the study, and the corresponding 95% confidence interval for this estimate, and examining whether the confidence interval lies completely above a value of 0.3 or not.

To test **Hypothesis 2**, comparisons between the average monthly symptom burden (measured by the monthly aggregate of symptom scores) resulting from no treatment/placebo/statin treatment periods will be made using a longitudinal multilevel model. The most basic model to test hypothesis 2 would be:

To test **Hypothesis 2**, we will calculate the nocebo ratio across all patients. This is to avoids attempting to analyse the pathological distributions that would arise for patient whose mean statin symptom score is close or less than their no treatment score, because the nocebo ratio becomes disruptively extreme. Combining the data

Confidential Page 14 of 22

SAMSON Protocol No: 1.4

Version 1.4 10th April 2020

across all patients to yield a single statin, placebo and no treatment symptom score allows a representative and interpretable nocebo ratio to be provided.

Hypothesis 3 is that the majority of patients will be taking statins, or have a non-side effect reasons for not doing so, at 6 months after study completion. This will be a descriptive statistic of the sample, which does not require inference of the population mean. No further statistical analysis is therefore necessary

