6.1. Primary outcome (Hypothesis 2)

Hypothesis 2: Overall >50% of symptom burden is nocebo rather than pharmacological.

For the trial, all participants receive a smartphone or, if they prefer, the application can be downloaded to their existing phone. Access to the phone will allow them to record real-time daily documentation of symptoms experienced on a visual analogue scale of 0-100.

Participants will rate symptoms every day, with the daily scores averaged into a monthly score.

SAMSON STATISTICAL ANALYSIS PLAN

January 14, 2020

Page 6

Each participant receives four months (4×28 days) each of no medication, placebo, and active medication (i.e, statin). We represent the individual participant's symptom score data as follows:

$$\begin{array}{ccc} x_{0_1} & x_{p_1} & x_{s_1} \\ x_{0_2} & x_{p_2} & x_{s_2} \\ x_{0_3} & x_{p_3} & x_{s_3} \\ x_{0_4} & x_{p_4} & x_{s_4} \end{array}$$

$$\bar{x}_0 = \frac{\sum_{j=1}^4 x_{0_j}}{4} = \frac{\sum_{j=1}^4 ((\sum_{i=1}^{28} x_{0_{ij}})/28)}{4}, \bar{x}_p = \frac{\sum_{j=1}^4 x_{p_j}}{4} = \frac{\sum_{j=1}^4 ((\sum_{i=1}^{28} x_{p_{ij}})/28)}{4}, \bar{x}_s = \frac{\sum_{j=1}^4 x_{s_j}}{4} = \frac{\sum_{j=1}^4 ((\sum_{i=1}^{28} x_{s_{ij}})/28)}{4}$$

\bar{x} - mean symptom score for no medication, placebo, statin, i -day 1 to 28 of treatment month, j - treatment month 1 to 4

We assume no carry-over effect. Thus, the estimated mean of the effect of nocebo is calculated as follows:

$$\text{Mean nocebo effect} = \sum_{n=1}^N \left(\frac{\bar{x}_{p_n} - \bar{x}_{0_n}}{\bar{x}_{s_n} - \bar{x}_{0_n}} \right) / N$$

N = number of study participants

Because the study participants are independent of each other, the variance of the estimated mean can be calculated as the sum of variances of the individual participants:

$$\text{Variance of the mean nocebo effect} = s^2 = \sum_{n=1}^N s_n^2 = \sum_{n=1}^N \text{Var} \left(\frac{\bar{x}_{p_n} - \bar{x}_{0_n}}{\bar{x}_{s_n} - \bar{x}_{0_n}} \right)$$

To calculate the variance of the estimate, we use a Taylor series approximation, which is a function of the variance of the numerator, variance of the denominator, and the covariance of the two:

$$1) \text{Var}(\text{numerator}) = \text{Var}(\bar{x}_p - \bar{x}_0) = s_p^2 + s_0^2 - 2r_{s_p, s_0} s_p s_0$$

$$2) \text{Var}(\text{denominator}) = \text{Var}(\bar{x}_s - \bar{x}_0) = s_s^2 + s_0^2 - 2r_{s_s, s_0} s_s s_0$$

CONFIDENTIAL

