$$3) \text{ Cov}(numerator, denominator) = \text{cov}(\bar{x}_p - \bar{x}_0, \bar{x}_s - \bar{x}_0) = \text{cov}(\bar{x}_p, \bar{x}_s) - \text{cov}(\bar{x}_p, \bar{x}_0) - \text{cov}(\bar{x}_0, \bar{x}_s) + \text{cov}(\bar{x}_0, \bar{x}_0) = \text{cov}(\bar{x}_p, \bar{x}_s) - \text{cov}(\bar{x}_p, \bar{x}_0) - \text{cov}(\bar{x}_0, \bar{x}_s) + s_0^2$$

$$\text{where, for example, } \text{cov}(\bar{x}_p, \bar{x}_s) = \frac{\sum_{j=1}^4 (x_{p_j} - \bar{x}_p)(x_{s_j} - \bar{x}_s)}{4 - 1}$$

$$4) s_n^2 = \text{Var}\left(\frac{\bar{x}_p - \bar{x}_0}{\bar{x}_s - \bar{x}_0}\right) = \left(\frac{\bar{x}_p - \bar{x}_0}{\bar{x}_s - \bar{x}_0}\right)^2 \left(\frac{\text{Var}(\bar{x}_p - \bar{x}_0)}{(\bar{x}_p - \bar{x}_0)^2} + \frac{\text{Var}(\bar{x}_s - \bar{x}_0)}{(\bar{x}_s - \bar{x}_0)^2} - 2 \frac{\text{cov}(\bar{x}_p - \bar{x}_0, \bar{x}_s - \bar{x}_0)}{(\bar{x}_p - \bar{x}_0)(\bar{x}_s - \bar{x}_0)}\right)$$

s = standard deviation, s² = variance, r = correlation

The Taylor's series approximation is based on asymptotic theory. Should the data not allow stable estimates of the components of the variance, we will use a bootstrapped estimate of the variance.

To calculate the 95% CI for the mean nocebo effect, the test statistic is $t = \sqrt{N}(\mu - \mu_0)/\sqrt{s^2}$

The null hypothesis is rejected if $t > t_{\alpha, N-1}$ where, in SAS, $t_{\alpha, N-1}$ is TINV(1- α , N-1);

In SAS, the p value associated with the test statistic T is PVAL=1-probt(abs(T), N-1) or PVAL=cdf('T', T, N-1).

The 95% confidence interval is $\text{Mean nocebo effect} \pm t_{\alpha/2, N-1} \sqrt{s^2} / \sqrt{N}$

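### Participants with one usable month per condition enter the primary mean at full weight, under a variance formula that assigns them zero variance

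*SAP*

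**What the plan says.** **Entry.** SAP 6.1.1 calculates a participant's nocebo effect if symptom scores are available "for at least one month of each treatment". Condition means are formed by "only using study months that have at least 10 of daily symptom scores non-missing". The sensitivity analyses change the number of days per month (14 and 16 are given as examples). None changes the number of months per condition.

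**Weighting.** SAP 6.1 assumes the full design: "Each participant receives four months (4×28 days) each of no medication, placebo, and active medication". The primary estimate is the plain average of individual ratios, with "N = number of study participants" as divisor.

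**Variance.** SAP 6.1 states that "the variance of the estimated mean can be calculated as the sum of variances of the individual participants". Each participant's variance is a Taylor approximation built from month-to-month variances and covariances. The covariance is written over months 1 to 4 with divisor 4 - 1, and no form is given for fewer months. The fallback is a bootstrap, "Should the data not allow stable estimates of the components of the variance". What triggers it and what is resampled are not stated.

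**Protocol.** Section 8 of version 1.4 first says that the comparison of conditions "will be made using a longitudinal multilevel model". No equation for that model appears in the text available. A second paragraph on Hypothesis 2 then adopts one ratio pooled over all patients, because individual ratios behave badly when the statin mean is close to or below the no-treatment mean. The SAP, dated January 2020 and based on protocol 1.2, keeps individual ratios and says in its opening section that it prevails where the two differ.

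**The concern.** The rule for who enters and the rule for how precision is measured do not fit together. The first accepts participants with far less data than the second was written for. Those participants have the least reliable ratios, yet they count as much as a twelve-month completer and are credited with little or no variance. As more of them enter, the primary mean becomes less stable while its computed standard error goes down. No planned sensitivity analysis would show this.

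Incomplete follow-up has to be planned for. Hypothesis 1 sets its threshold at 30% completion, and protocol 8.1 hypothesises 50% or more and bases power on about 70%. The primary analysis must therefore work for people who leave early or record few scores.

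**Working it through.** The plan gives no figure for this point. It has no month-to-month SD, no effect size and no expected number of one-month participants. The checks below use the SAP formulas as printed, with assumed inputs where needed.

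**1. Variance term by number of months.** Let the monthly scores in one condition have variance σ², and let m months be usable. The SAP shows the divisor 3 for the covariance and sets the covariance of a mean with itself equal to its variance, so the same divisor carries over. The expected printed term is (m - 1)σ²/3. The real variance of a mean of m independent months is σ²/m.

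| m | printed term | real variance of the mean |
|---|---|---|
| 1 | 0 | σ² |
| 2 | 0.33σ² | 0.50σ² |
| 3 | 0.67σ² | 0.33σ² |
| 4 | σ² | 0.25σ² |

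The printed term rises with more data, where the real one falls. With divisor m - 1 the one-month term is 0/0.

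**2. One month in every condition.** Take assumed monthly means of 8 (none), 15 (placebo) and 17 (statin). The ratio is (15 - 8)/(17 - 8) = 0.78. All deviations are zero, so the literal variance is 0; with divisor m - 1 it is undefined.

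**3. How such participants arise.** For a random 4/4/4 order with complete consecutive months:
- Leaving after month 3 gives one month of each with probability (8/11)(4/10) = 0.29.
- Leaving after month 5, 79% qualify, and all of them have at least one single-month condition, since two of each needs six months.
- After month 6, 91% qualify and 74% of those have a single-month condition. After month 7 the figures are 97% and 44%.

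**4. Spread of one ratio.** Assume a statin-minus-none difference of 10, monthly SD 5, true share 0.50 and normal independent months. The simulated 95% range is about -0.3 to 1.3 with four months per condition and -3.6 to 4.6 with one. The ratio falls outside 0 to 1 in 16% and 45% of cases. About 5% of one-month ratios are off by 4 or more, and one off by 4 moves a mean of 60 by 4/60 = 0.07.

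**5. Primary mean, N = 60, same assumptions.** With no one-month participants the central 95% range is about 0.28 to 0.72. With six it is about -0.24 to 0.97, while the median printed standard error goes from 1.11 to 1.08. The tails are heavy, so the range limits move by about 0.1 between runs. The ratio of pooled condition means stays near 0.41 to 0.59.

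If k of 60 contribute zero and the rest are equal, the standard error is multiplied by √((60 - k)/60): 0.95 for k = 6 and 0.89 for k = 12. If each counted four times a four-month variance, as independent months imply, the factors would be √(78/60) = 1.14 and √(96/60) = 1.26.

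**6. Larger signal.** When the difference is four monthly SDs rather than two, the range of the mean moves only from 0.46–0.54 to 0.44–0.56 with six one-month participants.

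**7. Scale of the printed interval.** The SAP sums the individual variances, divides only by N in the interval, and does not divide monthly variances by 4. Its squared standard error is therefore 4N = 240 times the properly scaled one when N = 60 and all have four months, a factor of √240 = 15.5 in the standard error. Under the step 4 assumptions the printed interval covers the true value in 99% to 100% of runs with up to six one-month participants. With the scaling corrected, coverage is about 98% with none and about 84% with six.

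**The case against.** **The interval is not too narrow as printed.** A reader might infer from the zero terms that the reported confidence interval is too short. Step 7 shows the opposite: the other scaling faults dominate. This objection stands. What remains is that the zero terms shrink the interval wrongly, and that correcting the scaling alone would expose under-coverage.

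**An exactly zero variance is a special case.** It needs one usable month in all three conditions. With complete consecutive months that happens only on leaving after month 3, and then 29% of the time. This also stands. Single-month conditions are much commoner, however, and each understates the variance in part.

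**There is a bootstrap fallback.** An inestimable variance is a natural trigger for it, and resampling participants would remove the zero. But resampling months within a person who has one month per condition can only return the same data, so the variance is again zero. The SAP does not say which is meant.

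**Extreme ratios also occur with four months.** They come from denominators near zero, so the one-month rule aggravates the problem and is not its only source. The protocol's pooled ratio would largely avoid it, but the SAP omits that ratio and declares itself governing.

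**Study month.** A reader might also infer that ignoring study month biases the estimate. Order is randomised, so drift adds noise rather than systematic bias, and the documents give no drift. As an illustration, the difference in mean month index between two conditions has variance 13(1/4 + 1/4) = 6.5, against a contrast variance of 25 × 0.5 = 12.5. A drift of 0.5 point per month would add 0.25 × 6.5/12.5 = 13% to the variance of one person's contrast. Adjustment is a secondary gain in precision only.

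**Conclusion.** The concern holds in this form: the SAP admits participants for whom its variance formula is zero, understated or undefined, and gives their ratios full weight. With an effect of two monthly SDs, six one-month participants in 60 are enough to make the primary mean uninformative about the 50% threshold, while the computed standard error falls by a few per cent. With an effect of four monthly SDs the damage is slight. Effect, SD, true share, independence of months and the number of such participants are all assumptions, so the size is conditional. The mismatch between the entry rule and the variance formula is not. The documents do not support the stronger readings that the printed interval is too narrow, that every early leaver is treated as perfectly precise, or that drift biases the result.

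**What to change.** Amend the SAP as follows:
- Pre-specify, beside the stated mean of ratios, the ratio of condition means pooled across participants, as protocol section 8 describes. Alternatively take it from a multilevel model written out in the SAP (condition and study month fixed, participant random).
- Obtain its confidence interval from a bootstrap that resamples participants.
- Compute no within-person variance from fewer than two usable months per condition, and give the formula for two and three months. If the Taylor variance is kept, correct its scaling at the same time.
- Add a sensitivity analysis on the minimum number of months per condition, and report how many participants have one, two, three and four.
- Reconcile the SAP with the protocol's pooled ratio, and say which is primary.

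The cost is SAP text, one model or pooled calculation, and a bootstrap on data already being collected. The model brings assumptions (normality, common residual variance). The pooled ratio gives more influence to participants with larger symptom changes, so it answers a slightly different question from the mean of individual ratios, and the SAP should say so.

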6.2. Other efficacy outcomes

6.2.1. Hypothesis 1

Hypothesis 1: More than 30% of enrolled participants will complete the study.

- 1) Point estimate $\hat{p} = x/N$ where x is the number of participants who completed the study and N is the number of enrolled participants
- 2) Hypotheses: $H_0: \hat{p} = p_0$ and $H_A = \hat{p} > p_0$ where $p_0 = 0.3$
- 3) Test statistic $z = \frac{\hat{p} - p_0}{\sqrt{p_0(1-p_0)/N}}$
- 4) Reject null hypothesis if $z > z_\alpha$, where $z_{0.05} = 1.645$
- 5) 95% confidence interval: $\hat{p} \pm z_{\alpha/2} \sqrt{\hat{p}(1 - \hat{p})/N} = \hat{p} \pm 1.96 \sqrt{\hat{p}(1 - \hat{p})/N}$

6.2.2. Hypothesis 3

Hypothesis 3: At six months after completion of the study, at least 50% of the participants will either be taking statins or have declined statins for reasons other than perceived side effects.

This hypothesis will be tested in the same way as Hypothesis 1 above but setting $p_0 = 0.5$.

7. Characteristics of the population

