8.1 POWER CALCULATIONS

Hypothesis 1: We hypothesise that of the patients enrolling for the study, 50% or more will complete the study. Our intention is to report the proportion of patients completing the study and its 95% confidence interval. Based on the binomial principle, $SE_p = \sqrt{p \cdot q/n}$, the number of patients planned after the calculation below (50) will permit this proportion to be stated with a 95% confidence interval of $\pm 1.96\sqrt{\frac{1}{2} \cdot \frac{1}{2}/50}$. Thus the proportion will be reported with a margin of error of $\pm 14\%$

or smaller. If the long-run proportion of patients who would finish the study is ~70%, then a sample size of 50 gives 85% power to detect this at the 5% significance level.

Hypotheses 2 and 3: These hypotheses address the sample of participants and not the population at large. They therefore do not need a sample size calculations.

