3.2. Unscheduled visits

Unscheduled assessments are not performed unless participants develop adverse events that the chief investigator considers 'related' to the trial procedure or to atorvastatin therapy.

4. Sample size determination and power calculation**4.1. Sample size calculation – Hypothesis 2**

Each "effect of nocebo" will be a value which, for the sake of the calculation in the protocol, was assumed to be between 0 and 1. The study aims to report an average effect of nocebo for

the population that has a 95% CI of $\pm 10\%$. To achieve this, assuming a conservative scenario of individual-participant values scattered uniformly from 0 to 1 (i.e., $SD = 1/\sqrt{12} = 0.29$), the number of participants to be studied will need to be $\geq N$ where $0.29/\sqrt{N} \leq 0.10/1.96$ (i.e., $N > (1.96 \times 0.29/0.10)^2 = 36$). The investigators planned to recruit 50 participants. In all a total of 62 participants were screened and 60 were randomized.

5. Statistical analysis: general considerations and conventions

Descriptive and inferential statistics will be used to summarize results of the SAMSON study. Continuous variables will be summarized using the number of subjects (N), mean, SD, median, 25th and 75th percentiles, and minimum and maximum. Discrete variables will be summarized using counts and percentages.

Summaries will be provided for demographics, medical history, concomitant medications, and adverse events. For summaries of medical history, concomitant medications, and AEs, the Medical Dictionary for Regulatory Activities (MedDRA®) and the World Health Organization Drug dictionaries, as appropriate, will be used.

All data listings, summaries, and statistical analyses will be generated using SAS® Version 9.4 (or higher) or other validated software.

6. Efficacy analysis

As described in Section 2.3, the study has three hypotheses.

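### At the 60 participants randomised, the z-test for Hypothesis 1 has an exact one-sided size of 6.3% rather than 5%, and at 24 or 25 completers it rejects while the 95% interval beside it still includes 0.30 (minor)

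*SAP*

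**What the plan says.** SAP 6.2.1 estimates the completion proportion as completers divided by N, where "N is the number of enrolled participants". Step 3 is a score-type z statistic that uses the null variance with p0 = 0.3 and has no continuity correction. Step 4 is the decision: "Reject null hypothesis if" z exceeds 1.645, a one-sided 5% rule. Step 5 is a two-sided 95% Wald interval with multiplier 1.96. No decision role is given to that interval.

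SAP 4.1 states that "The investigators planned to recruit 50 participants" and continues: "In all a total of 62 participants were screened and 60 were randomized".

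Protocol section 8 decides Hypothesis 1 differently, by "examining whether the confidence interval lies completely above a value of 0.3 or not". It does not name the interval method. Protocol 8.1 uses the simple binomial standard error for its margin of error, which points to Wald.

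SAP section 1 says the SAP prevails where the two documents differ on analyses. SAP 6.2.2 tests Hypothesis 3 by the same method with p0 = 0.5.

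**The concern.** The SAP states a 5% error rate and uses a normal approximation to a binomial count. With N already known to be 60, the exact error rate of the rule can be calculated, and it should be close to, and preferably no more than, the stated figure. A test and an interval printed side by side should also not point in opposite directions without an explanation.

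Completion above 30% is one of three named study hypotheses. At a borderline count, the report could declare it met while the next line shows an interval that includes 0.30, and while the protocol's own criterion fails.

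**Working it through.** **Inputs.** p0 = 0.3, critical value 1.645, and 95% Wald interval with multiplier 1.96 (SAP 6.2.1). N = 60 randomised and 50 planned (SAP 4.1). I take enrolled to mean the 60 randomised.

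**The stated level.** The upper 5% point of the standard normal is 1.645, so 5% one-sided reproduces under the approximation that the SAP uses.

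**Cut-off of the z-test at N = 60.** The null standard error is sqrt(0.3 × 0.7 / 60) = 0.05916. Rejection needs x/60 > 0.3 + 1.645 × 0.05916 = 0.3973, so x > 23.84. The test rejects at 24 or more.

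**Exact size.** This is P(X ≥ 24) for X binomial with N = 60 and p = 0.3, which is 0.0632.

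**Test and intervals at each count (N = 60).** The Wald lower limit is p̂ − 1.96 × sqrt(p̂(1 − p̂)/60). CP is Clopper-Pearson.

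| Completers | z | z-test | Wald 95% lower | CP 95% two-sided lower | P(X ≥ x) at p = 0.3 |
|---|---|---|---|---|---|
| 23 | 1.409 | no | 0.260 | 0.261 | 0.1041 |
| 24 | 1.690 | reject | 0.276 | 0.276 | 0.0632 |
| 25 | 1.972 | reject | 0.292 | 0.291 | 0.0362 |
| 26 | 2.254 | reject | 0.308 | 0.306 | 0.0196 |

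Both two-sided intervals first clear 0.30 at 26. At 24 and 25 the test and the interval disagree.

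**Dependence on N.** The same rule gives these exact sizes:

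| N | Rejects at | Exact size |
|---|---|---|
| 50 | 21 | 4.8% |
| 58 | 24 | 4.3% |
| 59 | 24 | 5.2% |
| 60 | 24 | 6.3% |
| 61 | 25 | 4.4% |
| 62 | 25 | 5.4% |

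**The possible rules at N = 60.** Power is the exact binomial tail at the stated true completion rate.

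| Rule | Rejects at | Size | Power at 50% | Power at 70% |
|---|---|---|---|---|
| SAP z-test | 24 | 6.3% | 95.4% | >99.9% |
| Exact binomial, one-sided 5% | 25 | 3.6% | 92.2% | >99.9% |
| Two-sided 95% interval above 0.30 (Wald or CP) | 26 | 2.0% | 87.7% | >99.9% |

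The one-sided 95% Clopper-Pearson lower limit is 0.293 at 24 and 0.309 at 25, so it agrees with the exact one-sided 5% test.

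**Hypothesis 3 (p0 = 0.5, assuming 60 analysed).** The z-test rejects at 37 (z = 1.807), with exact size 4.6%. P(X ≥ 36) = 7.8%, so the exact one-sided 5% test has the same cut-off of 37. The two-sided Clopper-Pearson lower limit is 0.499 at 38 and 0.516 at 39, so an interval rule would need 39 (size 1.4%).

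**The case against.** Several counter-arguments have force.

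- **The SAP already has one decision rule.** Step 4 decides and step 5 is an estimate. A reader might infer that the SAP leaves two rival rules, or that its conflict with the protocol is unresolved. The documents do not support that, because SAP section 1 makes the SAP govern.
- **The mismatch is largely by design.** A one-sided 5% test puts 5% in the upper tail and a two-sided 95% interval puts 2.5% there. SAP 6.1 pairs them in the same way for Hypothesis 2. What remains is that the SAP does not tell the reader that the interval is descriptive.
- **The 6.3% is discreteness.** A reader might infer that the test is generally anti-conservative. The table by N shows otherwise: the size moves either side of 5%. The mid-p value at 24 of 60 is 0.0497, so a mid-p test would also reject there. But 60 is the number that the SAP itself records, and at that number the stated level is exceeded.
- **The protocol's interval method is not named.** Under a Wilson interval the lower limit at 25 is 0.3006, which just passes, so only 24 would conflict with the protocol. Under Wald, which Protocol 8.1 implies, both 24 and 25 fail.
- **Requiring 26 completers would change the level.** It lowers the level from one-sided 5% to one-sided 2.5%, and through SAP 6.2.2 it would also raise the Hypothesis 3 cut-off. That is not needed to repair the size.
- **The effect is small.** Hypothesis 1 is not the primary outcome. The chance of exactly 24 or 25 completers is 7.6% at a true completion rate of 50%, 0.25% at 60% and about 0.0005% at 70%.

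**Conclusion.** The point stands as a minor one. At N = 60 the test in SAP 6.2.1 rejects at 24 or more completers with exact size 6.3%, which is 1.3 percentage points above its stated level. At 24 and 25 it rejects while the two-sided 95% Wald interval includes 0.30 and the protocol's criterion, read as Wald, is not met.

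An exact test at the declared level changes the conclusion only at 24 of 60 (40%). The interval rule changes it at 24 and 25 (40% to 42%). Protocol 8.1 hypothesises completion of 50% or more and also considers about 70%, so neither count is likely.

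This rests on enrolled meaning the 60 randomised. If all 62 screened were counted, the size would be 5.4%. Hypothesis 3 is not inflated if all 60 are analysed.

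**What to change.** In SAP 6.2.1, replace the z-test in steps 3 and 4 with an exact binomial test at the declared one-sided 5% level. With 60 enrolled, this rejects at 25 or more completers. Report the one-sided 95% Clopper-Pearson lower limit as the deciding limit. In step 5, compute the two-sided 95% interval as Clopper-Pearson too, and label it descriptive.

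If the sponsor prefers the protocol's interval rule, state it openly as a one-sided 2.5% criterion: 26 or more of 60.

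In SAP 6.2.2, state the consequence for Hypothesis 3. With 60 analysed, the exact one-sided 5% test keeps the cut-off at 37, while a two-sided Clopper-Pearson rule would move it to 39. If fewer are analysed, recompute the cut-off.

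The cost is a few lines of SAP wording and no new data. Power for Hypothesis 1 at 50% completion goes from 95% to 92% under the exact 5% test, or to 88% under the interval rule.
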